1.0 Objectives / Specific Aims

More than 10 million Americans over 65 years of age have presbyphonia, which is characterized by agerelated vocal fold atrophy that impairs their ability to speak at a normal volume for a normal amount of
time. Surgery can be used to treat presbyphonia, but non-invasive methods (voice exercises) are preferred
given the general risks of surgery and anesthesia in older individuals. Vocal Function Exercises (VFE), the
predominate type of voice exercises used to treat presbyphonia, can improve voice quality, but the
outcomes remain suboptimal, with many patients unable to successfully communicate, leading to
frustration, social isolation and feelings of helplessness.

Importantly, voice exercises target vocal fold strengthening, but underutilizes a potentially crucial second pathway for intervention: strengthening the respiratory system. In addition to vocal fold integrity, adequate vital capacity (airflow) and subglottal pressure are crucial for voice production. Many clinicians do indeed devote time in their therapy sessions to 'breathing exercises' (diaphragmatic breathing) but these are not evidence-based, and they are unlikely to adequately strengthen respiratory muscles to impact the critical components of pulmonary function that effect voice. Therefore, a targeted approach to improve the function of the respiratory system through rigorous and clinically feasible respiratory training (training of the respiratory muscles) could augment VFE and improve voice efficiency and quality in patients with presbyphonia.

The potential of respiratory training to improve respiratory and voice outcomes in patients with presbyphonia is particularly relevant when one considers that the older population usually has coexisting age-related declines in respiratory function. The clinical impact of respiratory training could be high, since it is a low-cost/low-risk approach that can be used in clinic and at home, be delivered during voice therapy sessions, and have a synergistic effect with voice exercises.

There are two main types of respiratory training: inspiratory training, also called inspiratory muscle strength training (IMST), and expiratory training, also called expiratory muscle strength training (EMST). In this application, we propose a novel, proof-of-concept study to test whether the addition of either type of respiratory training to the standard of care voice therapy (voice exercises) enhances respiratory and voice outcomes. This study will permit, for the first time, the comparison between inspiratory and expiratory training. The theoretical framework is: inspiratory training strengthens the inspiratory muscles and thus increases both vital capacity and the ability to counteract passive recoil of the lungs, improving

the quantity of and control over the airflow available to drive the vocal folds. Expiratory training strengthens the expiratory muscles to expand the expiratory reserve volume and provide more airflow for voicing. Using pulmonary function tests and respiratory pressure measures, combined with voice assessments, we will specifically evaluate our hypotheses and determine the independent effects of inspiratory training and expiratory training on respiratory function and voice production. We will also evaluate the interaction between the type of respiratory training and a patient's baseline respiratory function. This will provide mechanistic information to guide the future selection of the type of respiratory training to augment voice therapy, to promote an impairment-specific intervention paradigm.

Forty-eight participants diagnosed with presbyphonia will be included in the study and will be stratified and blocked-randomized into one of the three intervention groups (two experimental groups and one control group), using a 3-parallel arm design: 1) inspiratory training (IMST) (experimental group), 2) expiratory training (EMST) (experimental group), or 3) voice exercises (VFE) (control group), delivered four times during a 60-minute therapy session. Monitored home practice will consist of 10 minutes of twice daily exercise for the duration of therapy. Participants from all three groups will carry on with their standard of care voice therapy with a certified SLP.

Specific Aim 1: To measure the effects of respiratory training on respiratory and voice outcomes in patients with presbyphonia. Hypothesis 1: The respiratory training groups (inspiratory and/or expiratory) will demonstrate greater improvement in respiratory outcomes, measured through pulmonary function tests and respiratory pressure measures, compared with the voice exercises-only group. Hypothesis 2: The respiratory training groups (inspiratory and/or expiratory) will demonstrate greater improvement in voice-related outcomes than the voice exercises-only group.

Secondary Aim 1: To assess the reliability of the ratings for subjective outcomes (videostroboscopy ratings and perceptual judgements of voice quality). Hypothesis 1: Intra-judge reliability will be of at least 80%. Hypothesis 2: Inter-judge reliability will be of at least 70%.

Specific Aim 2: To determine how baseline measures of respiratory function influence the effects of respiratory training (respiratory and voice outcomes). Hypothesis 1: inspiratory training will have maximal effect on patients with decreased maximum inspiratory pressure (MIP). Hypothesis 2: Expiratory will have maximal effect on patients with decreased maximum expiratory pressure (MEP).

This is an initial feasibility and mechanistic study that has the potential to reveal that respiratory training can significantly improve outcomes from voice therapy by acting in synergy with voice exercises. Currently,

much time is spent in voice therapy on subthreshold 'breathing exercises' that lack evidence. This project will provide guidance for evidence-based and theory driven approaches to leverage respiratory function to improve voice therapy. Conversely, negative findings from this study would indicate that respiratory function is ineffective and not a viable target for therapy in this patient population.

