
Sample Size Justification

We considered maximum phonation time (MPT) as the primary outcome measure for sample size calculation. This measure was chosen because 1) low MPT is a hallmark of patients with presbyphonia, and 2) MPT is directly affected by both the laryngeal and respiratory systems. To estimate the expected effect size between VFE and the I+IVFE and E+VFE groups, we considered MPT values from groups of an

elderly population with different glottal closure and spirometry profiles (49). Considering that a combined intervention (inspiratory or expiratory training combined with voice therapy) would address both laryngeal and respiratory deficits, and that a voice therapy-only intervention would directly address only the laryngeal deficits, we compared MPT between the no-deficit group (complete glottal closure and normal spirometry) and the respiratory-deficit group (complete glottal closure and altered spirometry)(49). Based on these values and the pooled standard deviations, the expected difference between our control and experimental groups would represent a large effect size. As for the withinsubjects effect, a study by Nam et al.(50) found a 33% increase in MPT following a respiratory training intervention program in young adult singers. This corresponds to a very large within-subjects effect size with values of d exceeding 1.2. For Aim 2, we will assess improvement in 2 ways: function (a MPT increase of 4 seconds, which has been associated with a positive perceived effect following voice therapy in older adults(51)) and patient perception of function (a Glottal Function Index (GFI) score decrease of 4 points). An increase of 4 seconds in MPT and a decrease of 4 points on the GFI instrument both correspond to medium-large effect sizes considering the reported standard deviations of these measures in older subjects and in patients with glottal insufficiency (5.1 and 4.5, respectively) (42, 52). Based on the reported studies, the expected effect size for within-subjects and between-subjects differences was set at d=0.90. To have an 80% power to detect an effect size of d=0.90 with an alpha of 0.1 (since this is a pilot study), 15 participants are needed in each group. To account for loss to follow-up (estimated 10% dropouts rate), up to 16 participants will be recruited for each group, 48 patients total.

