The paucity of evidence supporting the therapeutic benefit of respiratory training for patients with voice disorders is concerning considering their widespread use by speech language pathologists (SLPs) (58, 59). Despite the well documented relationship between the respiratory and laryngeal systems, evidence-based guidelines for respiratory training are non-existent in the field of voice therapy. This void represents a critical barrier to optimal care for patients with voice disorders, especially for patients with presbyphonia who have known respiratory declines due to aging.

Current breathing exercises used by SLPs, such as diaphragmatic breathing, increasing extent of thoracic expansion, and increasing period of expiratory airflow on phonemes /s, z, a, æ, i/(29, 60) have not been tested in clinical trials with voice patients. It is likely that most of these exercises are not adequately intensive, in terms of loading, to induce neuromuscular and hypertrophic changes necessary for improving

respiratory muscle strength. Despite this lack of evidence, many clinicians devote substantial time in their therapy sessions to these 'breathing exercises'. In-person therapy time with a SLP is already limited and therefore should not be spent on subthreshold 'breathing exercises', such as diaphragmatic breathing, that lack evidence. If respiratory training does improve function, it would give clinicians an alternative modality to substitute for less evidenced 'exercises' and change current practice by encouraging SLPs to administer an evidence-based respiratory training. In addition, results from this study would allow to identify profiles of patients likely to benefit from respiratory and more precisely from inspiratory or expiratory training, further promoting efficient and impairment-specific allocation of therapy time.

Conversely, negative findings from this study would raise questions about the relevance of respiratory training in patients with presbyphonia and help focus research as well as clinical practice on more effective treatment approaches. If adequately rigorous respiratory training does not produce sufficient improvement in vocal function, it would be a mandate to stop wasting treatment time on subthreshold 'breathing exercises'.

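### The aims read a negative result as proof that the target does not work, but a non-significant result in a superiority pilot of about 15 per arm may not exclude a useful benefit

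*Combined protocol and SAP*

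**What the plan says.** Section 1.0 (Objectives / Specific Aims) says "negative findings from this study would indicate that respiratory function is ineffective and not a viable target for therapy in this patient population". The same paragraph opens with "This is an initial feasibility and mechanistic study".

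Section 16.0 (Importance of the Knowledge to be Gained) describes the same outcome more cautiously: "negative findings from this study would raise questions about the relevance of respiratory training in patients with presbyphonia".

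Section 12.0 (Sample Size Justification) says "We considered maximum phonation time (MPT) as the primary outcome measure for sample size calculation", and "the expected effect size for within-subjects and between-subjects differences was set at d=0.90". The size follows from this: "To have an 80% power to detect an effect size of d=0.90 with an alpha of 0.1 (since this is a pilot study"), 15 per group are required, and 16 are recruited to allow for 10% dropout.

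Section 12.0 (Data Analysis Plan) provides a repeated-measures model with Tukey comparisons if the between-subjects effect is significant. It gives no between-group margin, equivalence or futility criterion, or interval rule for a negative finding. Its 4 s figure for MPT defines improvement in an individual patient for Aim 2.

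**The concern.** A superiority test that fails to reject does not show that the effect is absent or too small to matter. That needs an interval that excludes a stated worthwhile difference. Section 1.0 goes straight from negative findings to ineffectiveness, in a small trial designed to detect only a large effect. If the report followed that sentence, inconclusive data could be presented as evidence against respiratory training in presbyphonia. The document also attaches two different strengths of conclusion to the same result, and nothing in section 12.0 supports the stronger one.

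**Working it through.** **Inputs from section 12.0.** d = 0.90; alpha 0.1 (sidedness not stated); power 80%; 15 per group; three arms; SD of MPT 5.1 s, reported for older subjects and not as an SD of change; 4 s responder threshold for Aim 2.

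**Assumptions.** Two-sided alpha, normal data, and SD 5.1 s for the analysed quantity.

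**1. The plan's sample size.** n = 2(1.645 + 0.842)² / 0.90² = 15.3, or 16 after rounding up; the t-based figure is 15.99. With 15 per group, power is 79.4% (normal) or 77.6% (noncentral t). The stated 15 is therefore close to a two-sided calculation. One-sided alpha 0.1 would give 12, and two-sided 0.05 would give 20. At SD 5.1 s the sizing effect is 0.90 × 5.1 = 4.59 s.

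**2. Precision of one arm against VFE.** Half-width = critical value × SD × √(2/15).
- Unadjusted 90% CI: 1.701 × 5.1 × 0.365 = 3.17 s.
- Tukey, 10% familywise, 3 groups, 42 df: (2.984/√2) × 5.1 × 0.365 = 3.93 s.
- With 10% dropout, 16 × 0.9 = 14.4 per arm remain. At 14 the half-widths are 3.29 s and 4.08 s.

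An estimate near 3 s, just short of significance, would have an unadjusted upper limit near 6 s, above the sizing effect of 4.59 s. An unadjusted interval excludes 4 s only if the estimate is below about 4 − 3.17 = 0.83 s.

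**3. Missing a real 4 s difference.** d = 4/5.1 = 0.784. Power at 15 per arm is 67.4% unadjusted and 52.0% with Tukey, so the comparison is non-significant about 33% and 48% of the time.

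**4. How often a non-significant comparison still includes 4 s.** Simulated, one arm against VFE, 15 per arm, SD 5.1 s:

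| True difference | Unadjusted 90% | Tukey 90% |
|---|---|---|
| 0 s | 31% | 48% |
| 1 s | 47% | 66% |
| 2 s | 62% | 81% |

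**5. Sensitivity to the pre-post correlation r.** The plan does not state r. If change is analysed, SD = 5.1 × √(2(1 − r)). Share of non-significant unadjusted results that include 4 s:

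| r | SD of change | True 0 s | True 2 s |
|---|---|---|---|
| 0.3 | 6.03 s | 44% | 72% |
| 0.5 | 5.10 s | 31% | 62% |
| 0.7 | 3.95 s | 11% | 39% |
| 0.8 | 3.23 s | 2% | 13% |

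**6. Scale.** For the unadjusted 90% interval to exclude 4 s with 80% probability, the need is 2(1.645 + 0.842)² / (4/5.1)² = 20.1, or 21 per arm, if the true difference is 0. If it is 1 s, the need is 2(1.645 + 0.842)² / (3/5.1)² = 35.7, or 36 per arm.

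**The case against.** The sentence is rationale text in a paragraph that calls the study initial, and no rule in section 12.0 implements it. Section 16.0 is already hedged. Both points are fair, and they make this a matter of wording and interpretation, not of conduct. They do not make the section 1.0 inference correct.

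A reader might infer four stronger things that the documents do not support.

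- **That a non-significant result usually leaves 4 s open.** For a single unadjusted comparison at SD 5.1 s the share is below half at true differences of 0 and 1 s. It passes half nearer 2 s, or with Tukey limits once there is some true benefit. At a correlation of 0.7 or more the unadjusted share is a minority at true differences from 0 to 2 s.
- **That 4 s is the plan's between-arm benefit.** It is a within-patient threshold. All arms receive VFE, and controls do more VFE repetitions at home, so an individual gain and a difference between arms are separate quantities. Against the sizing effect of 4.59 s, the unadjusted shares fall to about 19%, 32% and 47% at true differences of 0, 1 and 2 s.
- **That section 16.0 would order respiratory training to be abandoned.** It says "If adequately rigorous respiratory training does not produce sufficient improvement in vocal function, it would be a mandate to stop wasting treatment time", but the sentence goes on to name subthreshold breathing exercises. It is aimed at existing practice, not at inspiratory or expiratory training, and its trigger is insufficient improvement, not non-significance. It is not part of this point.
- **That a limit below 4 s is enough for a negative conclusion.** With a small analysed SD (below about 3.2 s), an arm significantly better than VFE could have an upper limit below 4 s. A negative conclusion must also require non-significance.

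**Conclusion.** The concern holds in a limited form. The section 1.0 sentence is wrong as written: the design tests superiority at a large effect, no criterion for lack of benefit is stated, and a non-significant result may not exclude a useful difference. Whether it does depends on the estimate and its interval.

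The size is moderate and conditional. A true 4 s difference goes undetected about one time in three unadjusted, and about half the time with Tukey. The share of non-significant comparisons that leave 4 s open runs, at a true difference of zero, from 2% (r = 0.8) to 44% (r = 0.3) unadjusted. At SD 5.1 s it is 31%, or 48% with Tukey. All of this rests on two-sided alpha 0.1, normal data and 15 evaluable per arm; the 5.1 s SD is cross-sectional and may not describe the analysed quantity. The conclusion that the sentence over-reads a negative result does not depend on these figures.

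**What to change.** Replace the section 1.0 sentence with wording of the strength used in section 16.0, so that both sections draw the same conclusion from the same result.

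Add to the Data Analysis Plan, before outcome data by arm are examined, a statement along these lines: a training arm is concluded to lack useful benefit on MPT only if it is not significantly better than VFE and the upper Tukey confidence limit of its difference from VFE lies below a pre-stated between-group margin; otherwise the result is reported as inconclusive. The sponsor should choose and justify that margin as a between-group quantity and not carry over the 4 s responder threshold by default. The Tukey limits should be reported whether or not the between-subjects effect is significant, with their familywise level stated. The conclusion should be limited to MPT, because Aim 1 also covers other voice outcomes and respiratory outcomes.

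The cost is wording plus one pre-stated margin, with no change to design, sample size or patient procedures. The downside is that a negative trial will support a weaker statement and will sometimes have to be reported as inconclusive.

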2.0 Background

Presbyphonia is characterized by vocal fold atrophy and a gap between the vocal folds. It impacts more than 10 million Americans, inhibiting their ability to speak at a normal volume for a usual duration(1). Disability related to presbyphonia is increasing due to: 1) the large number of older adults who work and 2) the expanding population over 65(2). Currently, non-invasive rehabilitation targeting laryngeal function is the main treatment for presbyphonia, since surgery is associated with increased risk of negative outcomes in older individuals and often results in suboptimal voice quality(3-5). While voice exercises improve voice quality in patients with presbyphonia, many patients are unable to successfully communicate in their environment even after completing treatment, i.e., they are unable to be heard unless close to their conversational partner, cannot be heard in the setting of background noise, or are unable to produce normal utterance lengths without taking frequent pauses to breathe. Presbyphonia is a well-known cause of reduced quality of life and social isolation(1, 6-8).

Current therapeutic approaches underutilize a second pathway for intervention – strengthening the respiratory system. Adequate vital capacity (airflow) and subglottal pressure are necessary to drive voice production. While many clinicians devote substantial time in their therapy sessions to breathing exercises, specifically diaphragmatic breathing, these exercises are not evidence-based and are unlikely to adequately lead to neuromuscular and pulmonary function changes. Improving the respiratory support for speech through rigorous respiratory training would, in theory, augment voice exercises to increase vocal efficiency in patients with presbyphonia. The coexisting age-related declines in respiratory function (in lung elasticity, ribcage mobility and inspiratory and expiratory muscle strength) further support respiratory training's potential to improve respiratory and voice outcomes in patients with presbyphonia(9-12). Additionally, respiratory training is a low-cost/low-risk approach that patients can use in clinic and at home to improve clinical measures of respiratory muscle strength and pulmonary function(13, 14).

There are two types of respiratory training: inspiratory and expiratory. Inspiratory and expiratory training have different physiological targets and result in unique and specific changes to respiratory function(13). Inspiratory training increases vital capacity, specifically inspiratory volume, and inspiratory muscle strength, to counteract passive recoil from positive pressures(15-17). The improved respiratory function from inspiratory training would increase the amount of air to drive the vocal folds and allow for better control of airflow with the respiratory system (to compensate for the lack of vocal fold closure). Expiratory training increases vital capacity, specifically expiratory reserve volume, and expiratory muscle strength to allow for increased contraction of the rib cage and abdominal muscles, thus providing access to more air to drive the vocal folds(18, 19). The effects of increasing respiratory muscle strength, either inspiratory or expiratory, have never been studied in patients with presbyphonia. Such an investigation, as we are proposing, would improve our mechanistic understanding of the cross-system interaction for voicing between laryngeal and respiratory function, and indicate the potential for inspiratory or expiratory respiratory training as viable therapy modalities for patients with presbyphonia.

The objective of respiratory training is to strengthen the respiratory muscles using a hand-held pressure threshold device in which patients breathe in (inspiratory training) or out (expiratory training) forcefully to open a valve and allow air to flow. The overloading of the respiratory muscles activates the neuromuscular system beyond its normal level of activity and forces the system to adapt, which results in changes in muscle function(20). Previous studies confirm that respiratory training induces morphologic changes in the respiratory muscles. In a study by Ramirez-Sarmiento et al.(21), post-intervention biopsies were taken from the external intercostal muscles and the results revealed a 38% increase in the proportion of type I fibers and a 21% increase in the size of type II fibers (21). Inspiratory and expiratory training have also been found to improve maximum inspiratory pressure (MIP) and maximum expiratory pressure (MEP), respectively, as well as spirometry outcomes in different populations, including elderly individuals (15, 22). In the voice literature, inspiratory training studies have targeted increasing MIP to reduce dyspnea in patients with upper airway obstruction diseases such as paradoxical vocal fold movement disorder, recurrent laryngeal papilloma and bilateral abductor vocal fold paralysis (23-25). We were unable to find published research on voice quality outcomes from inspiratory training. As for expiratory training, three studies have assessed its effect on professional voice users with voice complaints (26-28). Improved subglottal pressure at loud intensity and reductions in vocal symptoms were found when combining voice therapy and expiratory training in patients with laryngeal irritation, edema, and/or benign vocal fold lesions(28).

The effects of respiratory training on voice outcomes have never been studied on patients with presbyphonia despite the declines in respiratory function that occur with aging. Both inspiratory and expiratory pressures can be reduced in elderly patients, yielding different impairment profiles (10). Since inspiratory muscles are crucial for increasing inspiratory lung volume and for counteracting expiratory pressures to enhance airflow control during sustained speech, increasing their strength appears to be a viable target to improve the loudness and duration of speech (29). However, some individuals may have difficulty generating sufficient subglottal pressure despite initiating phonation at high lung volume because of reduced ribcage compliance and lung recoil forces(11, 12). For those patients, early activation of the expiratory muscles might be the most effective strategy to increase vocal efficiency, by compressing the chest wall to a smaller volume and generating the required airway pressure for speech production (19, 30). These patients may optimally benefit from expiratory training. Although some patients may benefit from both inspiratory and expiratory training, there is a need to assess the individual effects of both interventions prior to testing their combined effect in a future study to understand the mechanism of action and optimize the use of therapy time. Thus, we propose to study how differences in patients' baseline respiratory function impacts intervention response, specifically which patients benefit from inspiratory training and which patients benefit from expiratory training.

The contributions of this study will be to: 1) assess the relevance of respiratory training when treating patients with presbyphonia; 2) determine the mechanistic respiratory and voice effects of respiratory training for patients with presbyphonia, and 3) identify profiles of patients likely to benefit from each type of respiratory training. These contributions would be significant as they would begin to provide speech language pathologists (SLPs) with evidence pertaining to rigorous respiratory training for presbyphonic patients. After the study results are validated, SLPs will be able to determine, based on their clinical assessment, which patients should undergo respiratory training and which modality would be maximally beneficial, inspiratory or expiratory training, or both. This would improve the outcomes and efficiency of voice therapy. If respiratory training results in meaningful voice quality changes for patients with presbyphonia, it may also indicate a novel modality for use with other hypofunctional voice disorders (e.g. adductor paralysis).

